APPENDIX I: PERFORMANCE STATUS SCALES/SCORES

Performance Status Criteria					
Karnofsky and Lansky performance scores are intended to be multiples of 10					
ECOG (Zubrod)		Karnofsky		Lansky*	
Score	Description	Score	Description	Score	Description
0	Fully active, able to carry on all pre-disease performance without restriction.	100	Normal, no complaints, no evidence of disease	100	Fully active, normal.
		90	Able to carry on normal activity, minor signs or symptoms of disease.	90	Minor restrictions in physically strenuous activity.
1	Restricted in physically strenuous activity but ambulatory and able to carry out work of a light or sedentary nature, e.g., light housework, office work.	80	Normal activity with effort; some signs or symptoms of disease.	80	Active, but tires more quickly
		70	Cares for self, unable to carry on normal activity or do active work.	70	Both greater restriction of and less time spent in play activity.
2	Ambulatory and capable of all self-care but unable to carry out any work activities. Up and about more than 50% of waking hours	60	Required occasional assistance, but is able to care for most of his/her needs.	60	Up and around, but minimal active play; keeps busy with quieter activities.
		50	Requires considerable assistance and frequent medical care.	50	Gets dressed, but lies around much of the day; no active play, able to participate in all quiet play and activities.
3	Capable of only limited self-care, confined to bed or chair more than 50% of waking hours.	40	Disabled, requires special care and assistance.	40	Mostly in bed; participates in quiet activities.
		30	Severely disabled, hospitalization indicated. Death not imminent.	30	In bed; needs assistance even for quiet play.
4	Completely disabled. Cannot carry on any self-care. Totally confined to bed or chair.	20	Very sick, hospitalization indicated. Death not imminent.	20	Often sleeping; play entirely limited to very passive activities.
		10	Moribund, fatal processes progressing rapidly.	10	No play; does not get out of bed.

The conversion of the Lansky to ECOG scales is intended for NCI reporting purposes only.

APPENDIX II. MEDICATIONS ASSOCIATED WITH PROLONGED QTC

For the most current list of medications, please refer to the following website:

<http://www.azcert.org/medical-pros/drug-lists/drug-lists.cfm> .

Drugs that are generally accepted as having a known risk of causing Torsades de pointes Prohibited within one week of vorinostat on Arm C	Drugs that are generally accepted as having a possible risk of causing Torsades de pointes Use with caution in patients on Arm C
Amiodarone (Cordarone®, Pacerone®)	Alfuzosin (uroxatral®)
Anagrelide (Agrylin®, Xagrid®)	Atazanavir (Reyataz®)
Arsenic trioxide (Trisenox®)	Bedaquiline (Sirturo®)
Astemizole (Hismanal®) (Off US market)	Clazapine (Clozaril®)
Azithromycin (Zithromax®, Zmax®)	Dolasetron (Anzemet®)
Bepriidil Vascor® (Off US mkt)	Eribulin (Havalen®)
Chloroquine (Aralen®)	Famotidine (Pepcid®)
Chlorpromazine (Thorazine®)	Felbamate (Felbatol®)
Cisapride (Propulsid®) (Off US mkt)	Fingolimod (Gilenya®)
Citalopram (Celexa®, Cipramil®)	Foscarnet (Foscavir®)
Clarithromycin (Biaxin®)	Fosphenytoin (Cerebyx®)
Disopyramide (Norpace®)	Gatifloxacin (Tequin®)
Dofetilide (Tikosyn®)	Femifloxacin (Factive®)
Domperidone (Motilium®) (Not on US mkt)	Granisetron (Kytril®)
Dronedarone (Multaq®)	Iloperidone (Fanapt®)
Droperidol (Inapsine®) (not on US mkt)	Indapamide (Lozol®)
Droleptan, (Dridol®)	Isradipine (Dynacirc®)
Erythromycin (E.E.S.®)	Lapatinib (Tykerb®)
Escitalopram (Cipralext®, Lexapro®)	Levofloxacin (Levaquin®)
Flecainide (Tambocor®)	Lithium (Eskalith®)
Halofantrine (Halfan®)	Mirtazapine (Remeron®)
Haloperidol (Haldol®)	Moxepril/HCTZ (Uniretic®)
Ibutilide (Corvert®)	Nicardipine (Cardene®)
Levomethadyl (Orlaam®) (Off US mkt)	Nioltinib (Tasigna®)
Mesoridazine (Serentil®) (Off US mkt)	Ondansetron (Zofran®)
Methadone (Dolophine®)	Ofloxacin (Floxin®)
Moxifloxacin (Avelox®, Avalox®)	Oxytocin (Pitocin®)
Pentamidine (NebuPent®, Pentam®)	Paliperidone (Invega®)
Pimozide (Orap®)	Pasireotide (Signifor®)
Probuco (Off US mkt) Lorelco®	Promethazine (Phenergan®)
Procainamide (Pronestyl®, Procan®)	Quetiapine (Seroquel®)
Quinidine (Quinaglute®, Duraquin®)	Ranolazine (Ranexa®)
Sevoflurane (Ulane®)	Rilpivirine (Edurant®)
Sotalol (Betapace®)	Risperidone (Risperdal®)
Sparfloxacin (Zagam®) (Off US mkt)	Saquinavir (Invirase®)
Terfenadine (Seldane) (Off US mkt)	Sertindole (Serlect) off US mkt
Thioridazine (Mellaril®)	Sunitinib (Sutent®)
Vandetanib (Caprelsa®)	Tacrolimus (Prograf®)
	Tamoxifen
	Telvancin (Vibativ®)
	Telithromycin (Ketek®)
	Tizanidine (Zanaflex®)
	Tolterodine (Detrol®)
	Vardenafil (Levitra®)
	Venlafaxine (Effexor®)
	Voriconazole (Vfend®)
	Vorinostat (Zolinza®)
	Ziprasidone (Geodon®)

APPENDIX III. VORINOSTAT DOSING NOMOGRAM

For patients unable to swallow capsules, vorinostat will be given as a 50 mg/mL extemporaneous liquid preparation (see section 6.1.5 for compounding instructions) rounded to the nearest 10 mg according to the following dosing nomogram.

Patients who are able to swallow capsules may receive vorinostat capsules instead of suspension if their calculated vorinostat dose is within +/- 10% of a 100 mg increment (eg. 100 mg, 200 mg, 300 mg, or max dose 400 mg). Otherwise, they will need to receive vorinostat as suspension and dosed according to the following dosing nomogram.

Body Surface Area (m ²)	Vorinostat 180 mg/m ²
0.3-0.35	60 mg
0.36-0.39	70 mg
0.4-0.45	80 mg
0.46-0.55	90 mg
0.56-0.59	100 mg
0.6-0.65	110 mg
0.66-0.69	120 mg
0.7-0.75	130 mg
0.76-0.79	140 mg
0.8-0.85	150 mg
0.86-0.89	160 mg
0.9-0.95	170 mg
0.96-1.05	180 mg
1.06-1.09	190 mg
1.1-1.15	200 mg
1.16-1.19	210 mg
1.2-1.25	220 mg
1.26-1.29	230 mg
1.3-1.35	240 mg
1.36-1.39	250 mg
1.4-1.45	260 mg
1.46-1.55	270 mg
1.56-1.59	280 mg
1.6-1.65	290 mg
1.66-1.69	300 mg
1.7-1.75	310 mg
1.76-1.79	320 mg
1.8-1.85	330 mg
1.86-1.89	340 mg
1.9-1.95	350 mg
1.96-2.05	360 mg
2.06-2.09	370 mg
2.1-2.15	380 mg
2.16-2.19	390 mg
≥ 2.2	400 mg

APPENDIX IV: QUALITY CONTROL FOR FREE IODINE IN ¹³¹I-MIBG (DETECTION OF RADIOLYTIC DECOMPOSITION)

Radiopharmaceutical ¹³¹I-MIBG from DraxImage or NDP

Preparation Receipt of therapeutic ¹³¹I-MIBG from supplier

Materials Waters Accell Plus CM Sep-Pac
Ethanol
Sterile water
10 ml test tubes

Instrumentation Capintec well counter
Calculator

Procedure

1. Using a Waters Accell Plus CM SepPac cartridge, wet the sepPac with 5 ml ethanol. The long tip of the SepPac must be connected to the flushes
2. Rinse with 5 ml sterile water
3. Add one drop to 1/20 mL MIBG to SepPac. Dilute to around 0.5 uCi
4. Flush SepPac with 5 ml sterile water into a 10 ml test tube (flush tube)
5. Place cartridge into a second 10 ml test tube (A)
6. Place the cartridge tube into a well counter and record (A), set counter on 131-I
7. Count both tubes (A and flush) in the well counter, add counts together and record (B), set counter on 131-I
8. $(A/A+B \times 100 = \% \text{ tagged})$. Must be greater than 95% for DraxImage product and greater than 93% for NDP product - compare to TLC

Comments Procedure must be performed within 24 hours of receipt of dose from supplier. Results of bound iodine should be greater than 95% for DraxImage product and greater than 93% for NDP product. Record results on worksheet. Contact physicians if there is an aberrant or low result.

All centers administering MIBG therapy must perform an assay for radiolytic decomposition. The above is a suggested technique. Other techniques may be used provided they meet institutional radiopharmaceutical guidelines.

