Radiopurity is checked by both suppliers prior to shipment. Free radioiodine content is to be re-checked at the treating center prior to infusion according to the methods in Appendix IV and should be < 5% for ¹³¹I-MIBG from DraxImage and < 7% for ¹³¹I-MIBG from NDP.

The therapeutic dose of ¹³¹I-MIBG will be infused intravenously over 1.5-2 hours on day 1 of therapy with appropriate hydration, radiation isolation, thyroid blocking with potassium iodide and bladder protection with a Foley catheter.

The patient will remain in a radiation protected isolation room until radiation emissions meet institutional/state guidelines. This usually takes 3-5 days and then the patient can be discharged.

Patients should be transfused as needed to achieve a documented hemoglobin on the day of or one day prior to ¹³¹I-MIBG administration of ≥ 10 g/dL.

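### Appendix IV, steps 7 and 8: the tagged-percentage formula counts the cartridge twice, so it cannot exceed 50% against limits of 95% and 93%

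*Combined protocol and SAP*

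**What the plan says.** Section 4.3.1 requires a check at the treating center before infusion: "Free radioiodine content is to be re-checked at the treating center prior to infusion according to the methods in Appendix IV". It adds that free radioiodine "should be < 5% for ¹³¹I-MIBG from DraxImage and < 7% for ¹³¹I-MIBG from NDP".

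Appendix IV describes a cartridge procedure in numbered steps. The ones that matter here are:

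- Step 4: "Flush SepPac with 5 ml sterile water into a 10 ml test tube (flush tube".
- Step 5 puts the cartridge into a second tube, labelled A.
- Step 6: "Place the cartridge tube into a well counter and record (A), set counter on 131-I".
- Step 7: "Count both tubes (A and flush) in the well counter, add counts together and record (B".
- Step 8 prints the percentage tagged as A/A+B × 100, with no inner brackets, and sets the limit: "Must be greater than 95% for DraxImage product and greater than 93% for NDP product - compare to TLC".

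The comments below the steps oblige every center giving MIBG therapy to run an assay for radiolytic decomposition. They call this particular procedure a suggestion and permit others that meet institutional guidelines. Results go on a worksheet, and physicians are to be contacted about an aberrant or low value.

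Sections 6.2 (NDP product) and 6.3 (DraxImage product) also cite Appendix IV. They name thin layer chromatography, HPLC or another standardized institutional method, and give minimum purities at the treating center of 93% and 95% respectively.

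**The concern.** Steps 7 and 8 do not fit together. Step 7 makes B the sum of both tubes. Step 8 uses B as though it were the flush tube alone, and so adds the cartridge count a second time. The percentage that comes out is not the share of ¹³¹I bound to MIBG and cannot be read against the limits printed in the same step.

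This is a pre-infusion release calculation, and it is the only procedure the protocol works through step by step. A laboratory that followed it literally would record a failing value for good product, with an instruction to call physicians about a low result. For NDP product the timing is awkward: Section 6.2 places the test after thawing (for all but one named center) and requires infusion within 4 hours of thawing. A percentage recorded from a locally repaired formula could also not be checked later against the written procedure.

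**Working it through.** **Inputs, all from Appendix IV**

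- A = count of the cartridge tube (steps 5 and 6). Its place in the numerator of step 8 shows that it stands for the tagged activity.
- F = count of the flush tube (step 4), the activity not retained.
- B = A + F (step 7).
- Limits: above 95% (DraxImage) and above 93% (NDP) (step 8).

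**Reading of the formula.** Taken by strict operator precedence, A/A + B × 100 equals 1 + 100B. That is not a percentage and does not depend on the tagged share, so it cannot be meant. With the implied brackets it is A/(A+B) × 100, which is the reading used here.

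**Algebra.** Let T be total counts and t the true tagged share. Then A = tT, F = (1 − t)T and B = A + F = T. So

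A/(A+B) = A/(2A+F) = tT/(tT+T) = t/(1+t).

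This rises with t and reaches its maximum at t = 1, where it equals 1/2.

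**Numbers, with T = 10,000 counts for illustration (T cancels)**

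| True share t | A | F | B (step 7) | A/(A+B), step 8 | A/B |
|---|---|---|---|---|---|
| 1.00 | 10,000 | 0 | 10,000 | 50.0% | 100% |
| 0.99 | 9,900 | 100 | 10,000 | 49.7% | 99% |
| 0.97 | 9,700 | 300 | 10,000 | 49.2% | 97% |
| 0.95 | 9,500 | 500 | 10,000 | 48.7% | 95% |
| 0.93 | 9,300 | 700 | 10,000 | 48.2% | 93% |

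**Can the plan's limits be reached?** Setting t/(1+t) = L gives t = L/(1 − L).

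- L = 0.95: t = 0.95/0.05 = 19.
- L = 0.93: t = 0.93/0.07 = 13.3.

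A share cannot exceed 1, so neither limit is attainable.

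**Loss of scale.** The two limits are 2 points apart. On the step 8 scale, product at exactly those purities differs by 48.7 − 48.2 = 0.5 points.

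**Check of the two repairs.** With B = A + F, A/B = tT/T = t. With B redefined as F, A/(A+B) = tT/(tT + (1 − t)T) = t. Both return the true share, and both limits become attainable.

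**The case against.** The strongest reply is that this is a slip in an optional technique with little practical reach. Much of that stands. Appendix IV requires an assay, not this formula. Sections 6.2 and 6.3 name chromatography or another institutional method, and step 8 itself asks for comparison with TLC. The reference in Section 4.3.1 to the methods in Appendix IV carries with it the appendix's permission to use something else. A laboratory would probably notice values stuck at or below 50% on first use. The intended quantity is also clear, because the limits in Sections 4.3.1, 6.2, 6.3 and Appendix IV agree apart from strictness at the boundary.

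Three stronger readings are tempting, and the documents do not support them:

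- **Every dose in the trial would fail release.** This is true only of this calculation applied literally. A center using TLC, HPLC or another permitted method never meets the formula.
- **Every site must have silently corrected the formula, so the check differs between centers.** Nothing shows which sites used the cartridge method or what they did with it. Some variation in method is allowed by design, so it cannot be put down to this error.
- **Impure product could be released.** The error runs the other way. A result that cannot pass 50% can only reject product. Suppliers also check radiopurity before shipment (Section 4.3.1).

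What the reply does not do is make the arithmetic right. Brackets lost when the PDF was read would not cure it either, because the fault lies in step 7's definition of B, which is given in words. No other section corrects it.

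**Conclusion.** The formula is wrong as written. With B as step 7 defines it, step 8 returns at most 50% whatever the purity, against limits of more than 95% and more than 93%. A site that applies it literally would reject every dose, and it would not release impure product. The practical effect is limited to sites using the suggested cartridge technique. Sample size, error rates, the selection rule, endpoints and analyses are untouched.

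The conclusion rests on two assumptions: that step 8 is meant as A/(A+B), the only reading that yields a percentage, and that the cartridge count represents the tagged activity, as the numerator implies.

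**What to change.** Reconcile steps 7 and 8 so that total counts enter the denominator once. Either of these will do, and they are algebraically the same:

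- keep step 7 and change step 8 to percentage tagged = A/B × 100; or
- change step 7 so that B is the flush count alone, and print step 8 with brackets as A/(A+B) × 100.

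The release limits stay as stated, and no clinical rule changes. The cost is a one-line correction to the appendix, with no identifiable downside.

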APPENDIX V: COMPOUNDS THAT INTERFERE WITH MIBG METABOLISM AND UPTAKE

Drugs Known To Reduce Uptake of MIBG

Drug	Mechanism
Sympathomimetics	Depletion of storage vesicle contents.
Phenylephrine	These drugs occur in numerous non-prescription decongestants and diet aids. Their use should be excluded.
Phenylpropanolamine	
Pseudoephedrine, ephedrine	
Antihypertensive / cardiovascular	Inhibition of catecholamine uptake. Depletion of storage vesicle contents.
Labetalol	Depletion of storage vesicle contents. Inhibition of vesicle active transport.
Reserpine	
Calcium-channel blockers	Uncertain (also enhances retention of previously stored norepinephrine and MIBG by blocking Ca ⁺⁺ mediated release from vesicles)
Tricyclic antidepressants	Inhibition of catecholamine uptake
Cocaine	Inhibition of catecholamine uptake

Drugs Expected To Reduce Uptake of MIBG

Drug	Mechanism
Sympathomimetics	Depletion of storage vesicle contents.
Amphetamine and related compounds [#]	
Beta-sympathomimetics	Inhibition of catecholamine uptake.
Dobutamine, Dopamine, Metaraminol [#] :	
Systemic use. Effect unlikely with aerosol administration	
Atypical antidepressants	Inhibition of catecholamine uptake.
Maprotiline	
Trazodone	Inhibition of catecholamine uptake
Antipsychotics (major tranquilizers)	
Phenothiazines*	
Thioxanthines	
Butyrophenones	Depletion of storage vesicle contents. Competition for transport into vesicles.
*Occasionally used as antiemetic / antipruritic agents	
Antihypertensive / cardiovascular	Depletion of storage vesicle contents. Competition for transport into vesicles.
Adrenergic neuron blockers	

APPENDIX VI: ADJUSTED BODY WEIGHT CALCULATION

For patients whose actual body weight exceeds Ideal Body Weight (IBW) by more than 20%, the dose of stem cells, ¹³¹I-MIBG, vorinostat, and irinotecan may be based on Adjusted Body Weight (ABW) rather than actual body weight.

IBW Formulas:

1-17 yrs: height is in cm, weight is in kg

$$\text{IBW} = (\text{height}^2 \times 1.65) / 1000$$

1-17 yrs and 5 feet or taller:

$$\text{IBW in kg (male)} = 39 + (2.27 \times \text{height in inches over 5 feet})$$

$$\text{IBW in kg (female)} = 45.5 + (2.27 \times \text{height in inches over 5 feet})$$

18 yrs and older:

$$\text{IBW in kg (male)} = 50 + (2.3 \times \text{height in inches over 5 feet})$$

$$\text{IBW in kg (female)} = 45.5 + (2.3 \times \text{height in inches over 5 feet})$$

ABW is determined:

$$\text{ABW} = \text{IBW} + 0.4 \times (\text{Actual BW} - \text{IBW})$$

(Reference: Bone Marrow Transplant. 2007; 40(7):665-9)

APPENDIX VII. PATIENT INSTRUCTIONS FOR TREATING DIARRHEA

Be aware of your/your child's bowel movements. At the first sign that they are becoming softer than usual or if your child has any increase in the number of bowel movements over what is normal for him/her, start treating with loperamide (Imodium). **If he/she does not start taking the loperamide right away, the diarrhea may become severe and last several days or require hospitalization.**

Please follow these directions carefully, using dosing guidelines below:

- Take _____ loperamide at the first sign of diarrhea.
- Continue taking _____ loperamide every _____ hours until your normal pattern of bowel movements returns. Repeat the same doses and frequency if the diarrhea returns.
- Do not give more than _____ of loperamide in a 24 hour period.
- Please call your doctor if you have any questions about taking loperamide, if your child's diarrhea is not under control after two days, or if he/she is feeling extremely weak, lightheaded, or dizzy.
- Make an extra effort to give your child lots of fluids (several glasses of pedialyte, fruit juices, soda, soup, etc.) while your child is participating in this study.
- Side effects may include tiredness, drowsiness, or dizziness. If your child experiences these side effects, or if your child is urinating less frequently than usual, please contact your child's physician.
- Do not give your child any laxatives without consulting with his/her physician.

Loperamide dosing guidelines:

Loperamide 1 teaspoon = 1mg; 1 caplet = 2mg

Maximum dose of loperamide per day: < 6 years: 4mg/day; 6-11 years: 6mg/day; >11 years: 16 mg/day, using the non silicone-containing product.

Weight: > 43 kg: 4 teaspoons or 2 caplets (4 mg) after the first loose bowel movement, followed by 2 teaspoons or 1 caplet (2mg) every 2 hours. During the night the patient may take, 2 caplets (4mg) every 4 hours rather than 1 caplet (2mg) every 2 hours.

Weight: 30kg – 43kg: 2 teaspoons or 1 caplet (2mg) after the first loose bowel movement followed by 1 teaspoon or one-half caplet (1 mg) every 2 hours. During the night the patient may take, 1 caplet (2 mg) every 4 hours rather than one-half caplet every 2 hours.

Weight: 20kg – < 30kg: 2 teaspoons or 1 caplet (2mg) after the first loose bowel movement followed by 1 teaspoon or one-half caplet (1mg) every 3 hours. During the night, the patient may take 1 caplet (2mg) every 4 hours rather than one-half caplet every 3 hours.

Weight: 13kg - < 20kg: 1 teaspoon (1mg) after the first loose bowel movement followed by 1 teaspoon (1mg) every 3 hours. During the night, the patient may take 1 teaspoon (1 mg) every 4 hours rather than every 3 hours.

[figure not shown]
Weight: < 13kg: Half teaspoon (0.5mg) after the first loose bowel movement followed by half teaspoon every 3 hours. During the night, the patient may take half teaspoon (0.5mg) every 4 hours rather than every 3 hours.

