5.4 Management of Irinotecan-Associated Diarrhea

Diarrhea can be profuse and can occur either early (minutes to hours) or late (days) in the treatment schedule. Early diarrhea results from cholinergic stimulation, while late diarrhea relates to bacterial processing of irinotecan metabolites.

Early diarrhea: Patients who have the onset of diarrhea during the irinotecan infusion or in the hours following the completion of an irinotecan infusion should receive atropine (suggested dose 0.01mg/kg IV, maximum dose 0.4 mg). Prolongation of the irinotecan infusion to 90 minutes may be beneficial. Early onset diarrhea is usually accompanied by cholinergic manifestations (diaphoresis and abdominal cramping). Since irinotecan is being administered on a prolonged schedule (daily x 5) it may become difficult to distinguish early vs. late diarrhea. If a patient with presumed early diarrhea does not improve with administration of atropine, they should be instructed to begin treatment for late diarrhea.

Late diarrhea (more than 24 hours after irinotecan administration): Patients will be given Loperamide for late diarrhea based on body weight (according to the chart below). If late diarrhea occurs at home after the last dose of irinotecan is given, each family will be instructed to have antidiarrheal medication available and begin treatment at the first episode of poorly formed or loose stools or the earliest onset of bowel movements more frequent than normally expected for the patient. Patients will also be instructed to contact their physician if any diarrhea occurs. Patients and families will be given the instruction sheet in Appendix VII.

Loperamide dosing recommendations for late diarrhea

Loperamide 1 teaspoon = 1 mg; 1 caplet = 2 mg

Maximum dose of loperamide per day: < 6 years: 4 mg/day; 6-11 years: 6 mg/day; >11 years: 16 mg/day, using the non silicone-containing product.

Weight: > 43 kg: 4 teaspoons or 2 caplets (4 mg) after the first loose bowel movement, followed by 2 teaspoons or 1 caplet (2 mg) every 2 hours. During the night the patient may take, 2 caplets (4 mg) every 4 hours rather than 1 caplet (2 mg) every 2 hours.

Weight: 30kg – 43kg: 2 teaspoons or 1 caplet (2 mg) after the first loose bowel movement followed by 1 teaspoon or one-half caplet (1 mg) every 2 hours. During the night the patient may take, 1 caplet (2 mg) every 4 hours rather than one-half caplet every 2 hours.

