Weight: 20kg – < 30kg: 2 teaspoons or 1 caplet (2 mg) after the first loose bowel movement followed by 1 teaspoon or one-half caplet (1 mg) every 3 hours. During the night, the patient may take 1 caplet (2 mg) every 4 hours rather than one-half caplet every 3 hours.

Weight: 13kg - < 20kg: 1 teaspoon (1 mg) after the first loose bowel movement followed by 1 teaspoon (1 mg) every 3 hours. During the night, the patient may take 1 teaspoon (1 mg) every 4 hours rather than every 3 hours.

Weight: < 13kg: Half teaspoon (0.5 mg) after the first loose bowel movement followed by half teaspoon every 3 hours. During the night, the patient may take half teaspoon (0.5mg) every 4 hours rather than every 3 hours.

If there is failure of loperamide to control diarrhea after 24 hours of use, patients should receive **octreotide** (Sandostatin™) at the dose of **10 micrograms/kg/dose** subcutaneously every 12 hours x 3 days.

Because patients will be receiving prolonged exposure to antibiotics (i.e., cefixime or cefpodoxime), patients having significant diarrhea should have stool samples evaluated for *C difficile* toxin, as this is a potentially treatable cause of diarrhea. If patients have fever with diarrhea, or bloody diarrhea, evaluation of stools for bacterial culture should also be performed.

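### The Appendix VII family sheet sets the uncontrolled-diarrhea call at two days and omits the any-diarrhea call, a day later than Section 5.4's octreotide step

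*Combined protocol and SAP*

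**What the plan says.** Section 5.4 (Management of Irinotecan-Associated Diarrhea) applies to Arm B, the only arm given irinotecan. On contact it says: "Patients will also be instructed to contact their physician if any diarrhea occurs". The next sentence names the take-home document: "Patients and families will be given the instruction sheet in Appendix VII". It then moves to octreotide on this condition: "If there is failure of loperamide to control diarrhea after 24 hours of use".

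Appendix VII is that take-home document. It tells the family to start loperamide at the first change in stools and to carry on until stools are back to normal. Dose, interval and 24-hour limit are blanks for the site to fill in. The family is to call if the child's "diarrhea is not under control after two days".

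The sheet has other triggers. It asks for a call about loperamide questions, or for extreme weakness, lightheadedness or dizziness. A separate bullet asks for contact over tiredness, drowsiness or dizziness, or if the child passes urine less often. It contains no request to call for any diarrhea and none to call at 24 hours.

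Both places print the same weight-based dosing schedule under the same age-based ceiling: "Maximum dose of loperamide per day: < 6 years: 4 mg/day; 6-11 years: 6 mg/day; >11 years: 16 mg/day".

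**The concern.** The sheet is what a family has at hand when late diarrhea starts at home after the last irinotecan dose. Its explicit time limit for uncontrolled diarrhea is later than the protocol's own escalation point, and it omits the earlier contact that Section 5.4 intends. At stake is a delay in starting octreotide, and in the stool testing for *C. difficile* that Section 5.4 wants for significant diarrhea in these antibiotic-exposed patients.

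A second, smaller gap lies in the dosing. The weight schedule can reach the age ceiling well before the 24-hour point at which loperamide failure is judged. The sheet tells the family to stop there but does not prompt a call.

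**Working it through.** **Call timing.** The sheet starts loperamide at the first sign of diarrhea, so take both clocks as starting at the first dose.

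| Event | Section 5.4 | Appendix VII |
|---|---|---|
| Contact for any diarrhea | hour 0 | not stated |
| Loperamide judged to have failed | hour 24 (octreotide) | not stated |
| Call for uncontrolled diarrhea | covered by the hour-0 contact | hour 48 |

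Gap between the octreotide point and the sheet's call: 48 − 24 = 24 hours.

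**Dose ceiling.** The protocol gives no figure to reproduce here, so the schedules were run as printed. Let F be the first dose, D the repeat dose, I the interval in hours and M the daily maximum. On the daytime schedule:

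- amount scheduled before hour 24 = F + D × (24/I − 1)
- hour at which M is reached = I × (M − F)/D

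Inputs (F, D, I) by weight band:

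- Above 43 kg: 4, 2, 2 ("followed by 2 teaspoons or 1 caplet (2 mg) every 2 hours").
- 30–43 kg: 2, 1, 2.
- 20–<30 kg: 2, 1, 3.
- 13–<20 kg: 1, 1, 3 ("1 teaspoon (1 mg) after the first loose bowel movement followed by 1 teaspoon (1 mg) every 3 hours").
- Under 13 kg: 0.5, 0.5, 3.

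Night dosing is optional. In the 20–<30 kg band, for example, "the patient may take 1 caplet (2 mg) every 4 hours rather than one-half caplet every 3 hours", which can bring the ceiling forward. The last column gives the range when an assumed 8-hour night starts at hour 0, 6, 12 or 15, or when night doses are used throughout.

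| Weight, age | Scheduled before hour 24, daytime (mg) | M (mg) | Hour M reached, daytime | Range with night dosing |
|---|---|---|---|---|
| >43 kg, >11 y | 4 + 2×11 = 26 | 16 | 2×12/2 = 12 | 10–14 |
| 30–43 kg, 6–11 y | 2 + 11 = 13 | 6 | 2×4 = 8 | 6–10 |
| 20–<30 kg, 6–11 y | 2 + 7 = 9 | 6 | 3×4 = 12 | 8–12 |
| 20–<30 kg, <6 y | 9 | 4 | 3×2 = 6 | 4–6 |
| 13–<20 kg, 6–11 y | 1 + 7 = 8 | 6 | 3×5 = 15 | 15–20 |
| 13–<20 kg, <6 y | 8 | 4 | 3×3 = 9 | 9–12 |
| <13 kg, <6 y | 0.5 + 0.5×7 = 4 | 4 | 3×3.5/0.5 = 21 | 23–28 |
| 30–43 kg, >11 y | 13 | 16 | 2×14 = 28 | 28–30 |

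The heavier-for-age pairings reach the maximum sooner on the daytime schedule: 30–43 kg under 6 years at hour 4, >43 kg aged 6–11 at hour 2, and >43 kg under 6 at the first dose.

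Every pairing above 43 kg, and every pairing aged 11 or under at 13 kg or more, therefore reaches the ceiling before hour 24 under all the timings tried. Patients over 11 years at 43 kg or less do not. Below 13 kg and under 6 years, the ceiling is only just met at hour 21 on daytime dosing, with no scheduled dose blocked before hour 24.

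**The case against.** The strongest reply is that Section 5.4 requires two separate things: telling patients to make contact for any diarrhea, and handing over the sheet. A site that does both leaves the family with the earlier instruction, and nothing on the sheet forbids an earlier call. The sheet's other triggers, especially reduced urination, do not wait two days. This stands as mitigation, and the any-diarrhea point is an omission from the sheet and not a flat contradiction. It does not remove the mismatch. The sheet asks to be followed carefully and names a later time than the protocol's escalation step.

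On the ceiling, the sheet already says to stop, and Section 5.4 already fixes failure at 24 hours. That also stands. What remains is only the missing prompt to call.

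Three stronger readings are tempting, and the documents do not support them:

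- *The sheet instructs families to overdose.* It does not. The age maxima are printed, and there is a line for the 24-hour limit.
- *The protocol foresees diarrhea outlasting loperamide at home.* A reader might infer this from the sheet's warning of several days of diarrhea, or from the 72-hour rule in Section 4.8.2. The warning is conditional on loperamide not being started right away. Section 4.8.2 concerns the five days of irinotecan, which largely overlap the 3–5 days of isolation usual under Section 4.3.1. Neither shows how often treated diarrhea persists at home.
- *Many patients would hit the ceiling.* The documents give no weight-for-age data, so the result can be stated by age and weight pairing but not as a share of patients.

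**Conclusion.** The point holds as a minor supportive-care safety inconsistency in Arm B. For a family relying on the sheet alone, the call for uncontrolled diarrhea can come about 24 hours after Section 5.4's octreotide step. This assumes that the two days are counted from the start of loperamide and that none of the sheet's symptom triggers prompts an earlier call.

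The dose-ceiling gap is secondary. It assumes continuous dosing from hour 0 with diarrhea persisting, and the exact hours depend on when night dosing falls. The conclusion that the ceiling comes before hour 24 in the pairings named did not change under any timing tried.

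A reader should not infer any consequence for the trial's inference: the primary endpoint, sample size and selection rules are untouched.

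**What to change.** In Appendix VII:

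- Replace the two-day line with: *Call for any diarrhea, and call again no later than 24 hours after starting loperamide if it is not controlled.*
- Keep every other call trigger, including reduced urination.
- Add: *Call your doctor if the daily maximum is reached and diarrhea continues.*

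Whether reaching the maximum counts as loperamide failure before 24 hours is a clinical decision for the sponsor's clinicians. If they decide that it does, Section 5.4 needs one sentence saying so.

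The cost is a wording change and a reissued sheet for Arm B families, with no new data or visits.
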